### **6.1.1 Treatment**

Nemtabrutinib is administered as a daily 45 mg or 65 mg dose, taken orally, until disease progression, unacceptable toxicity, or another discontinuation criterion is met.

Each cycle consists of 4 weeks (28 calendar days). If a dose interruption or delay occurs or persists on Day 1 of planned next cycle the current cycle will be longer than 28 calendar days. If a dose interruption or delay occurs in the middle of the cycle and treatment can be resumed on Day 1 of planned next cycle, the current cycle will remain 28 days.

## **6.2 Preparation/Handling/Storage/Accountability**

### **6.2.1 Dose Preparation**

Nemtabrutinib will be administered QD by mouth under fasting conditions (either 1 hour prior to, or 2 hours after the meal). On visit days when PK and PD samples are scheduled, dosing should be delayed until the pre-dose PK and PD samples have been collected at the site.

For administrative reasons, the treatment period is divided into 4 week cycles (28 days).

### **6.2.2 Handling, Storage, and Accountability**

The investigator or designee must confirm appropriate temperature conditions have been maintained during transit for all study intervention received, and any discrepancies are reported and resolved before use of the study intervention.

Only participants enrolled in the study may receive study intervention, and only authorized site staff may supply or administer study intervention. All study interventions must be stored in a secure, environmentally controlled, and monitored (manual or automated) area in accordance with the labeled storage conditions with access limited to the investigator and authorized site staff.

The investigator, institution, or the head of the medical institution (where applicable) is responsible for study intervention accountability, reconciliation, and record maintenance (ie, receipt, reconciliation, and final disposition records).

For all study sites, the local country Sponsor personnel or designee will provide appropriate documentation that must be completed for drug accountability and return, or local discard and destruction if appropriate. Where local discard and destruction is appropriate, the

investigator is responsible for ensuring that a local discard/destruction procedure is documented.

The study site is responsible for recording the lot number, manufacturer, and expiry date for any locally purchased product (if applicable) as per local guidelines unless otherwise instructed by the Sponsor.

The investigator shall take responsibility for and shall take all steps to maintain appropriate records and ensure appropriate supply, storage, handling, distribution, and usage of study interventions in accordance with the protocol and any applicable laws and regulations.

### **6.3 Measures to Minimize Bias: Randomization and Blinding**

#### **6.3.1 Intervention Assignment**

Participants in this study will be allocated by nonrandom assignment.

An observation period of at least 24 hours will occur between intervention initiating treatment for the first and second participants enrolled within each new dose level. New dose level cohort will open for enrollment without delay once the DLT observation period (Cycle 1) of the current dose level cohort is completed and a dose-escalation decision is made.

#### **6.3.2 Stratification**

No stratification based on age, sex, or other characteristics will be used in this study.

#### **6.3.3 Blinding**

This is an open-label study; therefore, the Sponsor, investigator, and participant will know the intervention administered.

### **6.4 Study Intervention Compliance**

If there are interruptions in the study intervention schedule or infusion/injection was stopped, the details of and reason for any interruption or infusion/injection cessation of study intervention will be documented in the participant's medical record.

Interruptions more than 21 consecutive days from the protocol-specified treatment require consultation between the investigator and the Sponsor and written documentation of the collaborative decision on participant management.

- When participants self-administer study intervention(s) at home, compliance with study intervention will be assessed at each visit. Compliance will be assessed by counting returned tablets during the site visits and documented in the source documents and CRF. Deviation(s) from the prescribed dosage regimen should be recorded in the CRF.

- A record of the number of Nemtabrutinib dispensed to and taken by each participant must be maintained and reconciled with study intervention and compliance records. Intervention start and stop dates, including dates for intervention delays and/or dose reductions will also be recorded in the CRF.

## 6.5 Concomitant Therapy

Medications or vaccinations specifically prohibited in the exclusion criteria are not allowed during the ongoing study. If there is a clinical indication for any medications or vaccinations specifically prohibited, discontinuation from study intervention may be required. The investigator should discuss any questions regarding this with the Sponsor. The final decision on any supportive therapy or vaccine rests with the investigator and/or the participant's primary physician. However, the decision to continue the participant on study intervention requires the mutual agreement of the investigator, the Sponsor, and the participant.

Any medication or vaccine (including over-the-counter or prescription medicines, vitamins, and/or herbal supplements or other specific categories of interest) that the participant is receiving at the time of enrollment or receives during the study must be recorded along with:

- Reason for use
- Dates of administration including start and end dates
- Dosage information including dose and frequency

The Medical Monitor should be contacted if there are any questions regarding concomitant or prior therapy.

Note: Any licensed COVID-19 vaccine (including for Emergency Use) in a particular country is allowed in the study as long as they are mRNA vaccines, replication-incompetent adenoviral vaccines, or inactivated vaccines. These vaccines will be treated just as any other concomitant therapy. Investigational vaccines (ie, those not licensed or approved for Emergency Use) are not allowed.

Severe (Grade 3 and above) skin rashes considered to be related to nemtabrutinib may be treated with systemic steroids. Further details are provided in Section 6.6.1.

Concomitant use of anticoagulant or antiplatelet agents with BTKi increases the risk of major hemorrhage. Consider the risks and benefits of anticoagulant or antiplatelet therapy during study treatment. If anticoagulant or antiplatelet agents are used, participants should be monitored for signs and symptoms of bleeding.

Participants who are receiving HBV antiviral therapy at the treatment allocation should remain on antiviral therapy throughout study intervention and follow local guidelines for HBV antiviral therapy post completion of study intervention.

### 6.5.1 Prohibited Concomitant Medications

The following medications are not allowed during the screening and treatment phase of the study:

- Primary prophylactic G-CSF during the DLT evaluation period.
- Immunosuppressive therapies including continuous high-dose corticosteroids (>30 mg prednisone equivalent per day).
- Any concurrent anticancer therapy including, but not limited to, chemotherapy, radiotherapy (except palliative radiotherapy for local pain control), hormonal therapy or immunotherapy.
- Other investigational agents.
- Live or live attenuated vaccines within 30 days before the first dose of study intervention and while participating in the study.

NOTE: Any licensed COVID-19 vaccine (including for Emergency Use) in a particular country is allowed in the study as long as they are mRNA vaccines, replication incompetent adenoviral vaccines, or inactivated vaccines. These vaccines will be treated just as any other concomitant therapy. Investigational vaccines (i.e., those not licensed or approved for Emergency Use) are not allowed.

- Concomitant medications with the following characteristics are prohibited during the study (see Section 2.2.2.2 for DDI risk summary):
  - P-gp substrates with a narrow therapeutic index
  - CYP3A strong inducers
  - CYP3A strong inhibitors

Note: If the participant requires short-term use of CYP3A strong inhibitors, consultation with the Sponsor is required and treatment interruption with nemtabrutinib may be permitted.

Note: Detailed information of P-gp substrates with a narrow therapeutic index, CYP3A strong inducers and CYP3A strong inhibitors can be found at the following website:

<https://www.fda.gov/drugs/drug-interactions-labeling/drug-development-and-drug-interactions-table-substrates-inhibitors-and-inducers>

### 6.5.2 Rescue Medications and Supportive Care

Rescue treatment and adjuvant therapy are not specified in this study.

## 6.6 Dose Modification (Escalation/Titration/Other)

Nemtabrutinib – any treatment interruption more than 21 consecutive days needs to be discussed with the sponsor.

In or after cycle 4, participants receiving 45 mg of nemtabrutinib may be escalated to the higher dose if the tolerability is confirmed at the 65 mg of nemtabrutinib and at the discretion of the investigator after discussion with the participant, upon the consultation with sponsor.

If the escalation is permitted, the higher dose can be utilized from the Day 1 of next cycle based on the approved date.

The participants who receive the higher dose of nemtabrutinib should perform site visit / telephone contact after 14 ( $\pm 3$ ) days and 28 ( $\pm 3$ ) days from the first dose of the escalated dose to assess adverse event. Refer to Section 1.3 for the detailed schedule.

### 6.6.1 Nemtabrutinib Dose Modification

At the occurrence of an adverse event, associated with study treatment, dose interruptions and/or reductions in nemtabrutinib administration are allowed. If dose reduction is indicated, the participants should be assigned to the lower dose. In the event of a dose modification, the dose change(s) must be captured in the electronic data collection (EDC) system.

A maximum of 1 dose reduction will be allowed before a participant is discontinued from study treatment. Dose delays/reductions/modifications are specified in the event of non-hematological and non-skin toxicity (Table 6), hematological toxicity (Table 7, Table 8), and for drug-related skin toxicities (Table 9). Hematologic toxicity in CLL participants will be assessed by the grading scale in the iwCLL guidelines Appendix 11. Grade 1 to 2 drug-related skin rashes may be treated with topical steroids and antihistamines. Severe (Grade 3 and above) drug-related skin rashes may be treated with systemic steroids. Nemtabrutinib treatment should be discontinued in the case of a Grade 4 skin-related event.

Although the MOA for BTKi associated skin toxicities is not fully elucidated, several types of manifestations have been observed, including acne-like rash/folliculitis and immune-mediated drug reaction [Sibaud, V., et al 2020]. For acne-like rash, including papulopustular rash, obtaining bacteria/mycological cultures is recommended. If no microorganisms are detected, administer tetracyclines or other antibiotics as needed. If *Staphylococcus aureus* is detected, begin oral and/or topical antibiotics with anti-*Staphylococcus aureus* coverage.

Dosing interruptions are permitted in the case of medical/surgical events or logistical reasons (eg, elective surgery, unrelated medical events, radiotherapy) not related to study intervention. Consider the benefit-risk of withholding nemtabrutinib for 3-7 days pre-and post-surgery depending upon the type of the surgery and the risk of bleeding. Participants should be placed back on study intervention within 21 days of the scheduled interruption unless discussed with Sponsor. The reason for interruption should be documented in the participant's CRF and medical notes.

Participants should be monitored for signs and symptoms of bleeding during nemtabrutinib treatment. Discontinue nemtabrutinib if severe hemorrhage occurs.

Table 5 Dose Modification for Nemtabrutinib

Dose Modification	Dose of Nemtabrutinib	
0	45 mg QD (2 × 20 mg tablets plus 1 × 5 mg tablet)	65 mg (3 × 20 mg tablets plus 1 × 5 mg tablet)
1	30 mg QD (1 × 20 mg tablet plus 2 × 5 mg tablets)	45 mg QD (2 × 20 mg tablets plus 1 × 5 mg tablet)

Abbreviation: QD=once daily.

Table 6 Dose Delays/Reductions of Nemtabrutinib for Drug-related Non-Hematological and Non-skin Toxicity

Event Grade	Action
Grade 1 or 2	Continue current dose level; however, at the discretion of the investigator, dose interruption/modification may be implemented
Grade 3 (except Grade 3 nausea, vomiting, diarrhea, or controlled hypertension)	
Withhold nemtabrutinib until recovery to Grade 1 or baseline.
 
 
If recovery occurs within 21 days, restart nemtabrutinib at the same dose and schedule, unless further dose reduction is necessary in the opinion of the investigator.
 
If recovery occurs after more than 21 days on drug hold, permanently discontinue nemtabrutinib.
 
 
If, in the opinion of the investigator and with the agreement of the Medical Monitor, dose re-escalation to the dose modification 0 is in the best interest of a participant, the dose may be re-escalated after the participant is fully recovered.

Grade 4 (except Grade 4 nausea, vomiting, or diarrhea)	Permanently discontinue nemtabrutinib.
Grade 3 or 4 nausea, vomiting, or diarrhea	
Withhold nemtabrutinib until recovery to Grade 1 or baseline.
 
 
If recovery occurs within 24 hours, restart nemtabrutinib at the current dose level.
 
If recovery occurs after 24 hours and within 21 days, restart nemtabrutinib at dose modification 1.
 
If recovery occurs after more than 21 days on drug hold, permanently discontinue nemtabrutinib.
 
 
For any occurrence of nausea and vomiting, prophylactic anti-emetics may be used.
 
If, in the opinion of the investigator and with the agreement of the Medical Monitor, dose re-escalation to the dose modification 0 is in the best interest of a participant, the dose may be re-escalated after the participant is fully recovered.

Table 7 Dose Delays/Reductions of Nemtabrutinib for Drug-related Hematological Toxicity for All Participants Except Those with CLL

Event a	Action
Anemia (Hgb $\geq$ 8 g/dL)  Thrombocytopenia (Platelet $\geq$ 50 $\times 10^9$ /L)	Continue current dose level; however, at the discretion of the investigator, dose interruption/modification may be implemented.
Anemia (Hgb $<$ 8 and $\geq$ 6 g/dL)  Thrombocytopenia (Platelet $<$ 50 to $\geq$ 25 $\times 10^9$ /L)	
First occurrence of AE:
 
Withhold nemtabrutinib and monitor hematology and/or chemistry at least once a week until relevant lab value(s) recover to the values outlined below:
 
 
• If the relevant laboratory value recovers within 7 days to baseline (if cytopenias present at the start of study) or <math>\geq</math> 8 g/dL for Hgb, <math>\geq</math> 50 <math>\times 10^9</math>/L for platelets (if no cytopenias present at the start of study), resume nemtabrutinib treatment at the same dose level.
 
• If the relevant laboratory value takes more than 7 days but within 21 days to recover with or without therapy to the level described above, restart nemtabrutinib administration at dose modification 1.
 
• If recovery occurs after more than 21 days on drug hold, permanently discontinue nemtabrutinib.
 
 
Second occurrence of the Same AE:
 
 
• If a second hold is required for the same event, administer nemtabrutinib at dose modification 1.
 
• If a second hold is required for the same event at dose modification 1 and the event dose not recover within 21 days, permanently discontinue nemtabrutinib.
 
 
Third occurrence of the Same AE:
 
If a patient experiences a third occurrence of the same event at dose modification 1, permanently discontinue nemtabrutinib if not recovered within 21 days.

Event a	Action
Anemia (Hgb < 6 g/dL)  Thrombocytopenia (Platelet < 25×10  /L)  Neutropenia (ANC < 0.5×10  /L)	
First occurrence of AE:
 
Withhold nemtabrutinib and monitor hematology and/or chemistry at least once a week until relevant lab value(s) recover to the values outlined below:
 
 
If the relevant lab value recovers within 21 days to baseline (if cytopenias present at the start of study) or ≥ 8 g/dL for Hgb, ≥ 50×10^9/L for platelets, or ≥ 0.5×10^9/L for ANC (if no cytopenias present at the start of study), with or without the use of GCSF support, resume nemtabrutinib treatment at dose modification 1. If, in the opinion of the investigator and with the agreement of the Medical Monitor, dose re-escalation to dose modification 0 is in the best interest of a participant, the dose may be re-escalated after the participant is fully recovered.
 
If recovery occurs after more than 21 days on drug hold, permanently discontinue nemtabrutinib.
 
 
Second occurrence of the Same AE:
 
 
If a second hold is required for the same event at the dose modification 0 or 1 and the event does not recover within 7 days, permanently discontinue nemtabrutinib.
 

 Abbreviations: AE=adverse event; ANC=absolute neutrophil count; CLL=chronic lymphocytic leukemia; GCSF=granulocyte colony-stimulating factor; Hgb=hemoglobin
 
a. Applicable to participants who had new toxicities or participants with cytopenia at baseline that worsen.
	

Table 8 Dose Delays/Reductions of Nemtabrutinib for Drug-related Hematological Toxicity for Participants With CLL

Event a,b	Action
Grade < 2 Anemia (Hgb <50% decrease from baseline) and ≥6g/dL  Thrombocytopenia (platelet <50% decrease from baseline) and ≥25 × 10  /L	Continue current dose level; however, at the discretion of the investigator, dose interruption/modification may be implemented.
Grade 3 Anemia (Hgb 50% to 74% decrease from baseline) and <6 g/dL)  Thrombocytopenia (platelet 50% to 74% decrease from baseline) and <25 × 10  /L)	
First occurrence of AE:
 
Withhold nemtabrutinib and monitor hematology and/or chemistry at least once a week until relevant lab value(s) recover to the values outlined below:
 
 
If the relevant laboratory value recovers within 7 days to baseline (if cytopenias present at the start of study) or ≥8 g/dL for Hgb, ≥50×10^9/L for platelets (if no cytopenias present at the start of study), resume nemtabrutinib treatment at the same dose.
 
If the relevant laboratory value takes more than 7 days but within 21 days to recover with or without therapy to the level described above, restart nemtabrutinib administration at dose modification 1. If, in the opinion of the investigator and with the agreement of the Medical Monitor, dose re-
 

Event a,b	Action
	
escalation to dose modification 0 is in the best interest of a participant, the dose may be re-escalated after the participant is fully recovered.
 
 
• If recovery occurs after more than 21 days on drug hold, permanently discontinue nemtabrutinib.
 
 
Second occurrence of the Same AE:
 
 
• If a second hold is required for the same event at dose modification 0, administer nemtabrutinib at dose modification 1. Dose escalation to dose modification 0 is not permitted.
 
• If a second hold is required for the same event at dose modification 1 and the event does not recover within 21 days, permanently discontinue nemtabrutinib.
 
 
Third occurrence of the Same AE:
 
If a patient experiences a third occurrence of the same event at dose modification 1 and recovery does not occur within 21 days on drug hold, permanently discontinue nemtabrutinib.


Grade 4
 
Anemia (Hgb <math>\geq 75\%</math> decrease from baseline) and <math>< 6\text{g/dL}</math>
 
Thrombocytopenia (platelet <math>\geq 75\%</math> decrease from baseline) and <math>< 25 \times 10^9/\text{L}</math>
 
Neutropenia (ANC <math>< 0.5 \times 10^9/\text{L}</math>)
	
First occurrence of AE:
 
Withhold nemtabrutinib and monitor hematology and/or chemistry at least once a week until relevant laboratory value(s) recover to the values outlined below:
 
 
• If the relevant lab value recovers within 21 days to baseline (if cytopenias present at the start of study) or <math>\geq 8\text{ g/dL}</math> for Hgb, <math>\geq 50 \times 10^9/\text{L}</math> for platelets, <math>> 0.5 \times 10^9/\text{L}</math> for ANC (if no cytopenias present at the start of study), with or without the use of GCSF support following institutional standard practice, resume nemtabrutinib treatment at dose modification 1. If, in the opinion of the investigator and with the agreement of the Medical Monitor, dose re-escalation to dose modification 0 is in the best interest of a participant, the dose may be re-escalated after the participant is fully recovered.
 
• If recovery occurs after more than 21 days on drug hold, permanently discontinue nemtabrutinib.
 
 
Second occurrence of the Same AE:
 
If a second hold is required for the same event at dose modification 0 or 1 and the event does not recover within 7 days, permanently discontinue nemtabrutinib.

 Abbreviations: AE=adverse event; ANC=absolute neutrophil count; CLL=chronic lymphocytic leukemia; GCSF=granulocyte colony-stimulating factor; Hgb=hemoglobin.
 
a. Applicable to participants who had new toxicities or participants with cytopenia at baseline that worsens.
 
b. For participants with CLL, grading of hematological toxicities will be according to Appendix 11. Refer to additional notes in Appendix 11 when assessing grades.
	

Table 9 Dose Modification for Nemtabrutinib Drug-related Skin Toxicities

Event	Action
Grade 1 and 2	Continue current dose level; however, at the discretion of the investigator, dose interruption/modification may be implemented. Grade 1 to 2 drug-related skin rashes may be treated with topical steroids and antihistamines. For papulopustular rash oral antibiotic prophylaxis is strongly recommend.
Grade 3	
 
First occurrence of AE:               
 
➤ Withhold nemtabrutinib until recovery to Grade 1 or baseline; meanwhile treat the skin toxicity as clinically indicated; then restart nemtabrutinib at dose modification 1.
 
➤ If the event does not recur within 21 days after restarting the study treatment, the participant's treatment dose may be escalated to dose modification 0.
 
➤ If the event does not recur within 21 days after starting treatment, the participant may remain at this dose if, in the opinion of the investigator, the participant is getting clinical benefit at this dose level.
 
 
 
Second occurrence of AE:               
 
➤ If a participant experiences a second occurrence of the event while at dose modification 1, which is considered to be related to nemtabrutinib treatment, this participant should be permanently discontinued.
 
➤ If a participant experiences a second occurrence of the event at dose modification 0, which is considered to be related to nemtabrutinib treatment, withhold nemtabrutinib until recovery to Grade 1 or baseline; meanwhile treat the skin toxicity as clinically indicated; then restart nemtabrutinib at dose modification 1. Dose escalation to dose modification 0 is not permitted.
 
 
 
Third occurrence of AE:               
 
➤ Permanently discontinue study treatment.
 
 
 
 
Grade 3 drug-related skin rashes may be treated with systemic steroids.          For papulopustular rash oral antibiotic prophylaxis is strongly recommend.          Note: Participants with any grade Steven-Johnsons Syndrome should permanently discontinue nemtabrutinib.

Grade 4	Permanently discontinue study treatment. Grade 4 drug-related skin rashes may be treated with systemic steroids. For papulopustular rash oral antibiotic prophylaxis is strongly recommend.
Abbreviations: AE=adverse event.	

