#### Assessment of intensity/toxicity

- An event is defined as “serious” when it meets at least 1 of the predefined outcomes as described in the definition of an SAE, not when it is rated as severe.
- The investigator will make an assessment of intensity for each AE and SAE (and other reportable safety event) according to the NCI CTCAE, version 5.0. For hematologic toxicities in participants with CLL, assessment of intensity will be according to iwCLL in Appendix 11. Any AE that changes CTCAE/iwCLL grade over the course of a given episode will have each change of grade recorded on the AE CRFs/worksheets.
  - Grade 1: Mild; asymptomatic or mild symptoms; clinical or diagnostic observations only; intervention not indicated.
  - Grade 2: Moderate; minimal, local or noninvasive intervention indicated; limiting age-appropriate instrumental ADL.
  - Grade 3: Severe or medically significant but not immediately life-threatening; hospitalization or prolongation of hospitalization indicated; disabling; limiting self-care ADL.
  - Grade 4: Life threatening consequences; urgent intervention indicated.
  - Grade 5: Death related to AE.

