## 10.11 Appendix 11: iwCLL Criteria for Assessment of Hematologic Toxicities

In participants with CLL, hematologic toxicities will be assessed according to the following table (Table 14), based on the iwCLL Guidelines [Hallek, M., et al 2018].

Table 14 Chronic Lymphocytic Leukemia Hematologic Toxicity

Grade a	Decrease in Platelets b or Hemoglobin c (Nadir) From Treatment Value (%)	Absolute Neutrophil Count (u/L) (Nadir) d
0	No change to 10	≥2000
1	11 to 24	≥1500 and <2000
2	25 to 49	≥1000 and <1500
3	50 to 74	≥500 and <1000
4	≥75	<500

Source: [Hallek, M., et al 2018].

a Grades: 1=mild; 2=moderate; 3=severe; 4=life-threatening; 5=fatal. Death occurring as a result of toxicity at any level of decrease from baseline will be recorded as Grade 5.

b Platelet counts must be below normal levels for Grades 1 through 4. If, at any level of decrease, the platelet count is  $< 20 \times 10^9/L$ , this will be considered Grade 4 toxicity unless a severe or life-threatening decrease in the initial platelet count (eg,  $20 \times 10^9/L$ ) was present at baseline, in which case the participant is not evaluable for toxicity referable to platelet counts.

c Hemoglobin levels must be below normal levels for Grades 1 through 4. Baseline and subsequent hemoglobin determinations must be performed before any given transfusions. The use of erythropoietin is irrelevant for the grading of toxicity but should be documented.

d If the absolute neutrophil count (ANC) reaches  $< 1 \times 10^9/L$ , it should be judged to be Grade 3 toxicity. Other decreases in the white blood cell (WBC) count or in circulating granulocytes are not to be considered because a decrease in the WBC count is a desired therapeutic endpoint. A gradual decrease in granulocytes is not a reliable index in CLL for stepwise grading of toxicity. If the ANC was  $< 1 \times 10^9/L$  before therapy, the participant is not evaluable for toxicity referable to the ANC. The use of G-CSF is irrelevant for the grading of toxicity, but should be documented.

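### Table 8 joins a percentage fall and an absolute cut-off with 'and', so some severe cytopenias in CLL participants meet no dose-action row or carry a grade that differs from Appendix 11

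*Combined protocol and SAP*

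**What the plan says.** Section 6.6.1 gives separate hematological dose-modification tables: Table 7 for participants without CLL and Table 8 for participants with CLL. The anemia and platelet entries of Table 8 are:

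- **Continue row:** "Anemia (Hgb <50% decrease from baseline) and ≥6g/dL" and "Thrombocytopenia (platelet <50% decrease from baseline) and ≥25" (× 10^9/L).
- **Grade 3 row:** "Anemia (Hgb 50% to 74% decrease from baseline) and <6 g/dL" and "Thrombocytopenia (platelet 50% to 74% decrease from baseline) and <25" (× 10^9/L).
- **Grade 4 row:** a fall of 75% or more and below 6 g/dL (hemoglobin) or below 25 × 10^9/L (platelets). Neutrophils below 0.5 × 10^9/L also qualify, with no percentage condition.

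Footnote b of Table 8 says that CLL hematological toxicity is graded by Appendix 11. There, Table 14 grades platelets and hemoglobin by percentage fall alone (50 to 74 is Grade 3, 75 or more is Grade 4), provided that the value is below normal. Note b adds that a platelet count below 20 × 10^9/L, at any level of decrease, is graded as follows: "this will be considered Grade 4 toxicity unless a severe or life-threatening decrease in the initial platelet count" was already present.

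On bleeding, the text of 6.6.1 says: "Discontinue nemtabrutinib if severe hemorrhage occurs". Table 6 covers drug-related non-hematological, non-skin toxicity. For Grade 3 it requires withholding and then: "If recovery occurs within 21 days, restart nemtabrutinib at the same dose and schedule", unless the investigator judges a reduction necessary. Its listed exceptions do not include hemorrhage.

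**The concern.** A dose-modification table should give one row for each result a site can see. Table 7 does this: its hemoglobin cut-offs (8 and 6 g/dL) and platelet cut-offs (50 and 25 × 10^9/L) divide the whole range with no gap. Table 8 uses two conditions per row and pairs only the matching corners, small fall with high value and large fall with low value. The other two corners, large fall with a value above the cut-off and small fall with a value below it, are not assigned.

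Sites would then have to choose between the printed limits and the Appendix 11 grade, and the choice changes what happens to the participant. Section 2.3 lists cytopenias and hemorrhage among the risks to monitor. Discontinuation due to AEs is a primary endpoint. Under Section 4.3.1, missing more than 25% of Cycle 1 doses because of drug-related AEs is itself a DLT: 25% of 28 daily doses is 7, so 8 or more missed. Whether a site withholds can therefore affect the DLT count. With 3 evaluable participants, Table 2 moves from E at no DLT to S at one and D at two.

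**Working it through.** The plan states no figure to reproduce. The check asks whether the printed rows cover all results and agree with Appendix 11.

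**Inputs.** The Table 8 rows and the Table 14 grades are as above. The Table 3 entry floors are platelets 50 × 10^9/L and hemoglobin 8.0 g/dL, both waived with significant marrow involvement. The documents give no lower limits of normal; 12 g/dL and 150 × 10^9/L are assumed. Every nadir below is well under these.

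**Formula.** Percentage fall = 100 × (baseline − nadir) / baseline.

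| Baseline to nadir | Fall | Appendix 11 grade | Table 8 row as printed |
|---|---|---|---|
| Platelets 200 to 45 | 155/200 = 77.5% | 4 | none (not <25) |
| Platelets 200 to 60 | 140/200 = 70% | 3 | none (not <25) |
| Platelets 40 to 22 | 18/40 = 45% | 2 | none (fall <50%, value <25) |
| Platelets 60 to 18 | 42/60 = 70% | 4 (note b) | Grade 3 |
| Platelets 80 to 24 | 56/80 = 70% | 3 | Grade 3 |
| Hgb 14 to 6.5 | 7.5/14 = 53.6% | 3 | none (not <6) |
| Hgb 9.0 to 5.5 | 3.5/9.0 = 38.9% | 2 | none (fall <50%, value <6) |
| Hgb 10 to 4.5 | 5.5/10 = 55% | 3 | Grade 3 |

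**Where each gap can arise** (b = baseline):

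- Platelet fall of 50% or more, ending at 25 or above: needs 0.5b ≥ 25, so b ≥ 50. Every participant who meets the platelet floor without the waiver is in this range.
- The same with a fall of 75% or more (Grade 4 in Table 14): needs 0.25b ≥ 25, so b ≥ 100.
- The printed Grade 3 platelet row cannot be reached from b ≥ 100, because a fall under 75% then leaves more than 25.
- Platelet fall under 50%, ending below 25: needs 0.5b < 25, so b < 50. At entry this is possible only under the marrow-involvement waiver.
- Hemoglobin fall of 50% or more, ending at 6 or above: needs b ≥ 12.
- Hemoglobin fall under 50%, ending below 6: needs b < 12.
- Hemoglobin fall of 75% or more leaves less than 6 from any baseline below 24 g/dL, so Grade 4 hemoglobin has no gap in practice.

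**Extent on a grid.** Baselines were platelets 50 to 300 in steps of 1 and hemoglobin 8 to 16 in steps of 0.1. These are counts of possible value pairs, not expected frequencies in participants.

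- Platelets, Appendix 11 Grade 3: 10,724 of 10,914 pairs have no row (98%).
- Platelets, Grade 4: 5,151 of 10,985 (47%).
- Hemoglobin, Grade 3: 441 of 2,443 (18%).
- Hemoglobin, Grade 4: 0 of 2,397.
- Hemoglobin below 6 g/dL at any grade: 380 of 4,779 (8%).

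**Consequence of the grade mismatch.** For platelets 60 to 18 with recovery within 7 days, the Grade 3 row resumes the same dose and the Grade 4 row resumes at dose modification 1.

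**Hemorrhage, side by side.** Section 6.6.1 says to discontinue for severe hemorrhage, and Section 7.1 makes discontinuation permanent. Table 6 withholds a drug-related Grade 3 event and restarts it. Section 10.3.5 describes the grade as "Grade 3: Severe or medically significant but not immediately life-threatening", and the rash sentence in 6.6.1 glosses severe as Grade 3 and above. On that meaning, a drug-related Grade 3 bleed that recovers within 21 days falls under both rules.

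**The case against.** The best defense is footnote b. Table 8 rows carry grade labels and Appendix 11 sets the grade, so a site could reasonably take platelets 200 to 45 to the Grade 4 row. That would close much of the platelet gap. It does not settle the matter: the footnote does not lift the limits printed in the rows, and hemoglobin 9.0 to 5.5 is Grade 2 by Appendix 11 yet fails the continue row's 6 g/dL limit.

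Several stronger readings are tempting, and the documents do not support them:

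- **That severe cytopenia in CLL is generally left without a row.** Platelets 80 to 24, hemoglobin 10 to 4.5 and any neutrophil count below 0.5 × 10^9/L do map.
- **That sites have no guidance at all.** Section 6.6.1 opens by allowing interruption or reduction for treatment-associated AEs, and Section 7.1 lets the investigator discontinue for untoward effects.
- **That a Grade 4 platelet decrease is a DLT whenever it occurs, yet may prompt no dose action.** The Note in Section 4.3.1 says that with marrow involvement platelet numbers alone are not a DLT without new or worsening symptoms. The mismatch is narrower than the any-duration rule suggests.
- **That the hemorrhage rules are flatly opposed.** The protocol does not define severe hemorrhage. Section 10.3.5 describes Grade 3 as severe or medically significant, and Section 8.4.7 uses a different term, major hemorrhage, for bleeds of Grade 3 or higher. The event-specific sentence may be meant to govern, but no text says so.

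It is also fair that the trial is descriptive, enrolls about 6 to 12 participants of mixed histology, and calls CLL rare in Japan. Few participants may be touched, and the effect on any reported rate cannot be sized from the documents.

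**Conclusion.** The Table 8 defect stands as an internal inconsistency in a dosing rule. Followed as printed, it gives no row for platelet falls of 50% or more that stay at or above 25 × 10^9/L, for hemoglobin falls of 50% or more that stay at or above 6 g/dL, or for hemoglobin below 6 g/dL after a fall under 50% from a baseline below 12 g/dL. A smaller gap, platelet falls under 50% ending below 25, needs a baseline below 50. Some pairs also carry two grades with different restart actions. The case for correction rests on participants' dosing and on consistency across sites; no bias in a reported rate has been shown.

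This rests on reading the row conditions as joint, as the wording has it. For platelets 60 to 18 it also assumes that a baseline of 60, above the Table 3 floor, is outside the severe-baseline exemption in note b.

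The hemorrhage point is secondary and of lower severity. It is a conflict only for drug-related events, only if hemorrhage counts as non-hematological, and only if severe means Grade 3. The wording elsewhere suggests that meaning but does not fix it.

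**What to change.** Reconcile Table 8 with Table 14 and its notes so that every combination of percentage fall and absolute count maps to exactly one row, and the grade in Table 8 equals the Appendix 11 grade. State in footnote b whether the Appendix 11 grade or the printed row limits decide the action. The pairs tabulated above can serve as test cases.

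Separately, define severe hemorrhage, or refer to an existing definition, and state whether the hemorrhage sentence in 6.6.1 or the Grade 3 row of Table 6 governs.

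Which thresholds and actions are right is for the sponsor's clinicians; no view is offered here. The cost is wording in Section 6.6.1, aligned with Appendix 11, and a letter to sites. No procedure, visit or sample is added.
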